13.6 Analysis of Secondary Endpoints

Other secondary endpoints include other pain measures, breast cancer symptoms, and HRQOL which will be measured as described in sections 5 and 10. Scoring and handling of missing data will follow the user manual for the EORTC QLQ-C30 and QLQ-BR23. Analyses conducted at the final time point will be consistent with the analyses described in section 13.5. The change from discharge (T1) to follow-up (T3) will also be evaluated for all secondary measures that are measured at both timepoints.

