2.4 Rationale

Patients who have mastectomy and reconstructive surgery often experience discomfort from not only the surgical incisions, but also from the drainage tubes inserted at the incision sites. The tubes and drainage receptacles are often difficult to manage when patients are discharged from the hospital, wearing typical clothing and returning to regular daily activities.

Most women are able, at the time of mastectomy, to have breast reconstruction surgery to rebuild and contour breast shape. Post-operative care is more complex than mastectomy alone and requires an inpatient stay of two to four nights. The accumulation of fluid – a *seroma* – is a frequent complication following breast surgery and warrants the insertion of drainage tubes for prevention. In a review investigating techniques in the prevention and management of seromas after breast surgery, drains produced a significant reduction in seroma incidence.⁷ The number of drains depends on the type of surgery and preference of the surgeon and ranges from 2 for unilateral and from 4 for bilateral mastectomy.^{8,9} Patients after mastectomy and breast reconstruction experience soreness in the chest, underarm and shoulder, as well as numbness at the drainage site. Patients have reported the greatest discomfort at the drain insertion sites. The number of drains after mastectomy has also been associated with increased pain in the post mastectomy patient, although the number of drains was not associated with the rate or number of seromas.^{8,10} If axillary lymph nodes are removed, patients may experience some numbness in the arm and also are at risk for *lymphedema*,¹¹ a build-up of lymph that causes swelling in the arm, hand, breast, underarm, chest, trunk and/or back.

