10. STUDY CALENDAR

Measure	Inpatient Post Mastectomy (T1)	At Home Post-Discharge (T2)	Follow-up Clinic Appointment (T3)
Participant Demographics	X		
Pain Intensity Numeric Scale (0-10)	X	X	X
Pain Frequency and Intensity Symptom Distress Scores	X		X
Health Related Quality of Life			X
Breast Symptoms			X
Pain Management		X	
Post-Discharge Pain, Pain Management, Complications (Documented in Electronic Medical Record)			X
Participant Clinical Characteristics (Diagnosis, Treatment Regimen)			

Documented in the Medical Record)			
-----------------------------------	--	--	--

T1: First (or second) day post mastectomy, during inpatient stay
T2: Exclusive of day discharged and day of follow-up when all drains are removed, daily for 7-42 days
T3: Day of follow-up clinic appointment when all drains are removed

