13.5 Analysis of Primary Endpoints

All randomized patients will be included in all analyses. Minimal missing data is expected; therefore, in the event of missing data, no imputation will be performed. The analyzable sample for the primary endpoint includes participants who are randomized and have reported a pain score at T3 regardless of intervention use. The primary endpoint is pain intensity measured on the 0-10 scale at the follow-up clinic appointment (T3). The pain score will be summarized at each time point and plotted. The T3 pain score will be compared between UC and Jacki groups using a Wilcoxon rank sum test. Due to the nature of the pain measure (i.e., integers on a 0-10 scale), there will be ties in pain score, and the number of ties could affect the performance of the non-parametric test.

Depending on the structure of the data, a t-test may be considered with a possible transformation. Assumptions will be examined and a method selected prior to testing.

Additionally an analysis of covariance (ANCOVA) approach may be considered. Factors that may be associated with the T3 pain score (baseline score, time since discharge, unilateral vs bilateral mastectomy, number of post-surgical drains, neoadjuvant chemotherapy, axillary lymph node dissection, pain management at home with pain medication, and post mastectomy clothing) will be assessed univariately and then adjusted in a multivariable model. The change in pain over time will also be evaluated using linear mixed models.

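### Section 13.6 names no method for T1-to-T3 change in three secondary pain scores and leaves baseline adjustment optional; ANCOVA on T3 would be at least as precise as what is planned

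*Combined protocol and SAP*

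**What the plan says.** Section 5.1.3 schedules the two Symptom Distress pain items (frequency and intensity) and the three-item PROMIS Pain Intensity form at T1 and T3. PROMIS Pain Interference, the QLQ-C30 and the QLQ-BR23 are T3 only, so this point does not touch them.

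For the secondary endpoints, 13.6 makes two commitments:

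- A T3 analysis: "Analyses conducted at the final time point will be consistent with the analyses described in section 13.5". The committed arm comparison in 13.5 is: "The T3 pain score will be compared between UC and Jacki groups using a Wilcoxon rank sum test".
- A change analysis: "The change from discharge (T1) to follow-up (T3) will also be evaluated for all secondary measures that are measured at both timepoints". No estimator, model or test is named for it.

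Baseline adjustment appears in 13.5 only as an option: "Additionally an analysis of covariance (ANCOVA) approach may be considered". Baseline score is the first of eight candidate covariates listed there. Section 13.5 also says: "The change in pain over time will also be evaluated using linear mixed models".

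On timing, 13.6 attaches the word discharge to T1. The study calendar in section 10 says: "T1: First (or second) day post mastectomy, during inpatient stay". Section 13.1 describes T1 as pre-discharge, and section 2.4 says that post-operative care "requires an inpatient stay of two to four nights".

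**The concern.** For these three scores, the only use of the T1 value that the plan commits to is the T1-to-T3 change, and the method is left open. If the analyst takes the simplest route and compares T3 minus T1 between arms, T1 enters with a fixed weight of 1. When T1 and T3 are weakly correlated, that adds noise, and the comparison is less precise than one that ignores T1.

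A weak correlation is plausible here. T1 is taken on post-operative day 1 or 2, while drains are usually out at 7-14 days but sometimes as late as 42. Apart from the PROMIS item on current pain, the T1 items look back over a week that mostly precedes surgery. The T3 form asks patients to apply the same window to the time since they left hospital.

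At stake is the precision of three secondary comparisons, and an analysis choice that could be made after the data are seen.

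**Working it through.** **Inputs.** From 13.2: 130 evaluable patients, two-sided alpha 0.1, a 1.0-point difference and SD 2.2, all for the 0-10 pain scale. The allocation ratio is not stated; 1:1 (65 per arm) is assumed. The T1-T3 correlation r is not in the documents, so a range is shown. The standardized effect 1.0/2.2 = 0.4545 is borrowed from the primary endpoint as an illustration, because the plan gives no effect size for the secondary scores.

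**The plan's own figure.** Normal-approximation power is Φ(d·√(n/2) − 1.645). With n = 65 and d = 0.4545 it is Φ(2.591 − 1.645) = 82.8%. Multiplying n by the Wilcoxon efficiency factor 3/π gives 81.3%. Across the five SDs in the 13.2 table, the adjusted formula gives 92.7, 87.3, 81.3, 75.1 and 69.1%, against the stated 91, 86, 80, 74 and 68%. All are within 2 points, so the stated power reproduces.

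**Variance of the arm difference relative to T3 alone**, with equal variances at T1 and T3:

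- T3 alone: 1
- Unadjusted change: 2(1 − r)
- ANCOVA on T3 with T1 as covariate: 1 − r²

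Hence ANCOVA/change = (1 + r)/2, which is below 1 for every r below 1, and ANCOVA/T3 alone = 1 − r², which is never above 1. Change is noisier than T3 alone when r < 0.5 and more precise when r > 0.5.

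The ordering of ANCOVA and change does not need equal variances. With SDs s1 and s3, the change variance minus the ANCOVA variance is (s1² + s3² − 2r·s1·s3) − s3²(1 − r²) = (s1 − r·s3)², which is never negative. The one degree of freedom that ANCOVA spends on the covariate is ignored.

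**Illustrative power**, Φ(2.591/√V − 1.645), where V is the relative variance. All three columns use the plain normal formula, so they are comparable with each other:

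| r (assumed) | V change | V ANCOVA | Power, change | Power, T3 alone | Power, ANCOVA |
|---|---|---|---|---|---|
| 0.1 | 1.80 | 0.99 | 61.3% | 82.8% | 83.1% |
| 0.3 | 1.40 | 0.91 | 70.7% | 82.8% | 85.8% |
| 0.5 | 1.00 | 0.75 | 82.8% | 82.8% | 91.1% |
| 0.7 | 0.60 | 0.51 | 95.5% | 82.8% | 97.6% |

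**The T1 label.** Taking a stay of two to four nights as discharge on post-operative day 2 to 4, and T1 as day 1 or 2, the gap from T1 to discharge runs from 2 − 2 = 0 to 4 − 1 = 3 days.

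**The case against.** A reader might infer that 13.6 commits only to a raw change score. It does not. The preceding sentence commits to a T3 comparison, the change analysis is an addition to it, and the text never says that the change is unadjusted. The gap is an unnamed method, not a wrong one.

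A reader might also infer that a real difference would be missed, by setting 61% power for change against 83% for ANCOVA at r = 0.1. That contrast ignores the committed T3 comparison. Against T3 alone, ANCOVA gains 0.3 points at r = 0.1, 3.0 at 0.3, 8.3 at 0.5 and 14.8 at 0.7. Where change does worst, ANCOVA gains least over T3 alone; above r = 0.5, change itself beats T3 alone.

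Nor does the discharge label bias the arm comparison. Both arms share the T1 schedule, and the other sections place T1 correctly. Because most T1 items recall the past week, it would also be too simple to say that the change measures recovery from a post-operative day 1-2 state.

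One could reply that 13.5 already covers baseline through its ANCOVA and mixed models. That does not close the gap. The ANCOVA is optional, screens its covariates univariately, and includes candidates that arise after randomization (home pain medication and post-mastectomy clothing). The mixed-model sentence is not a final-time-point analysis, and those are all that 13.6 carries over.

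It stands that these are three secondary scores with no power claim, and that a linear model on 5-point items is an approximation.

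**Conclusion.** The point holds as a gap in specification with a cheap remedy. For three secondary pain scores, the plan commits to a T3 test that ignores baseline and a change analysis without a method, while the analysis at least as precise as both is left optional.

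That ordering does not depend on r; the size of the gain does. Relative to an unadjusted change score, ANCOVA's variance is 55% at r = 0.1, 75% at r = 0.5 and 85% at r = 0.7. Relative to T3 alone it is 99%, 75% and 51%. These figures assume equal variances at T1 and T3; the power figures also assume 65 per arm and the primary endpoint's standardized effect.

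The label on T1 is a separate wording error of about 0 to 3 days with no effect on the arm contrast. The primary analysis and the sample size are unaffected. Label: cheap improvement.

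**What to change.** In 13.6, replace the sentence on change with wording such as: *For secondary measures taken at T1 and T3, arms will be compared on the T3 score by ANCOVA with the T1 score of the same measure as covariate, using ranked scores if the coarse scale requires it. T1-to-T3 change will be summarized descriptively.* State that this is the arm comparison for these three scores; the Wilcoxon comparison can stay as a supporting result. Measures taken only at T3 keep the 13.5 approach.

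In the same sentence, refer to T1 as the post-operative day 1-2 assessment rather than discharge. Calling it an assessment avoids implying that the items describe only that day.

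The cost is SAP wording, with no new data and no extra patients. The downsides are a modelling assumption on coarse scores, which ranking eases, and a departure from strict consistency with 13.5 for these three scores, where ANCOVA is only optional.

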13.7 Reporting and Exclusions

13.7.1 Evaluation of Toxicity

Not applicable.

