7. ADVERSE EVENTS: LIST AND REPORTING REQUIREMENTS

7.1 Adverse Events

7.1.1.1 Adverse Event List for the Jacki Recovery Jacket

The Jacki has not previously been studied, and no adverse events or serious adverse events have been reported to A Little Easier Recovery® or at the enrolling study sites, which have previously provided jackets to some post-operative patients.

Potential adverse events include the following:

- 1.) A participant wearing the jacket may remove the jacket without first removing the drains from the pockets. This may cause pain and/or the drains to be dislodged, which would require a trip to the hospital to have them re-inserted. It could also lead to a greater risk of infection at the site of the drains.
- 2.) A participant wearing the jacket may become too warm in warm weather or may develop a skin reaction to the jacket, which is made of 50% cotton and 50% polyester.

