7.2 Adverse Event Characteristics

Adverse events are not graded.

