7.3 Expedited Adverse Event Reporting

7.3.1 Investigators **must** report to the Overall PI any adverse event that occurs while the subject is on study. The event must be reported to the Overall PI within 24 hours.

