7.4 Routine Adverse Event Reporting

All Adverse Events **must** be reported in routine study data submissions to the Overall PI on the clinical data forms. **AEs reported through expedited processes must also be reported in routine study data submissions.**

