13.7.2 Evaluation of the Primary Efficacy Endpoint

Efficacy will be established if a statistically significant difference of 1.0 or greater on the PINS is detected.

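### No section plans a by-arm summary of adverse events, although the protocol names drain dislodgement, re-insertion and drain-site infection as potential harms of the jacket

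*Combined protocol and SAP*

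**What the plan says.** Section 7.1.1.1 states that "The Jacki has not previously been studied". It describes one mechanism of harm specific to the jacket, namely taking it off with the drains still in its pockets: "This may cause pain and/or the drains to be dislodged, which would require a trip to the hospital to have them re-inserted", and "It could also lead to a greater risk of infection at the site of the drains". Overheating and skin reaction are listed second. The same section adds that no adverse events had been reported to the supplier or at the enrolling sites, some of whose patients had already received jackets.

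Collection is provided for. Section 7.3 requires "any adverse event that occurs while the subject is on study" to reach the Overall PI within 24 hours. Section 7.4 requires all adverse events to "be reported in routine study data submissions to the Overall PI on the clinical data forms". Section 12.2 has the PI review them and report to the IRB. Section 7.2 says "Adverse events are not graded". The calendar in section 10 lists complications among the items taken from the electronic medical record at T3.

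In the statistical section, the whole entry under "13.7.1 Evaluation of Toxicity" is that it does not apply. The next subsection gives the efficacy rule: "Efficacy will be established if a statistically significant difference of 1.0 or greater on the PINS is detected".

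**The concern.** The protocol identifies a plausible, device-specific route to an event that needs a hospital visit, and it randomizes against a control arm that is not given the jacket. A comparison by arm is the natural use of that design, because drains can come out and drain sites can become infected in either arm, and only the difference bears on the jacket. Nothing requires anyone to make that comparison. A report that followed the plan could present a pain benefit without saying how many participants in each arm had a dislodged drain, a re-insertion or an infection. For a garment with no earlier study, readers would want those counts beside the efficacy result.

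**Working it through.** **1. Does any section plan a by-arm analysis of harms?**

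- Objectives (1.2, 1.3): pain, HRQOL, breast symptoms, at-home pain patterns and management, and jacket use. No adverse event or complication.
- Primary analysis (13.5): T3 pain score only.
- Secondary analysis (13.6): other pain measures, breast symptoms and HRQOL. No adverse event or complication. The QLQ-BR23 items in Appendix A do cover pain, swelling, oversensitivity and skin problems in the affected breast area, and 13.6 analyses them at T3 in line with 13.5, that is, by arm. They do not cover dislodgement, re-insertion or infection.
- Interim monitoring (13.2, 13.4, 12.2): no interim analyses or stopping rules; PI review of adverse events, with no comparison by arm described.
- 13.7.1: not applicable. 13.7.2: PINS difference only.

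The answer is no.

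**2. Are the data for such a table secured?**

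Only partly. Section 10 lists complications in the T3 record review. Section 5.1.3 describes the post-discharge record review as covering pain and pain management only. Under the second description, dislodgement and infection would depend on adverse event reports alone. Those reports come from an unblinded trial in which one arm has been instructed about this hazard.

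**3. What could the table show?**

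The documents give no event rates, so the rates below are assumptions for illustration.

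Inputs: 149 enrolled and 130 evaluable (13.2). The allocation ratio is not stated; 1:1 is assumed, giving 74-75 randomized per arm. The enrolled number is the right base because the table covers all randomized participants. (149 × 0.87 = 129.6, consistent with the stated 130.)

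Upper bound on the event rate when an arm of size n has no events, 1 − α^(1/n):

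| n | one-sided 95%: 1 − 0.05^(1/n) | two-sided 95%: 1 − 0.025^(1/n) |
|---|---|---|
| 74 | 4.0% | 4.9% |
| 75 | 3.9% | 4.8% |

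With 5 events in 74 (6.8%), the exact (Clopper-Pearson) 95% interval is 2.2% to 15.1%.

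Chance of at least one event in an arm of 74, 1 − (1 − p)^74: 52% at p = 1%, 78% at 2%, 98% at 5%.

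Power of a two-sided 0.05 Fisher exact test at 74 per arm, by enumerating both binomial distributions:

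| Assumed rates | Power |
|---|---|
| 2% vs 5% | 5% |
| 5% vs 10% | 13% |
| 2% vs 10% | 40% |
| 5% vs 15% | 44% |

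The intervals are informative enough to report. A significance test is not informative enough to rely on.

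**The case against.** The strongest reply is that the entry is probably a template leftover. Dose-limiting toxicity, dose modification, pharmaceutical information and antitumor effect are marked the same way, and for a jacket there is no drug toxicity to evaluate. That is a fair reading, and nothing in the entry forbids tabulating adverse events. A reader might infer that the investigators decided against comparing harms; the documents do not support that. What remains is that no other section supplies the analysis.

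Second, safety is handled operationally: 24-hour reporting, routine forms, PI review, an off-study criterion for an unsafe device (5.8), and instruction in the Jacki arm on taking the drains out of the pockets first (5.1.2). The supplier and the sites had no reported events. All this stands. It rebuts any suggestion that harms are ignored and it limits the severity, but none of it yields a comparison by arm.

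Third, an efficacy rule need not mention harms. That is correct, so 13.7.2 is not itself at fault.

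Three further inferences should be resisted. One is that a large excess would stand out once tabulated: at 2% vs 10% or 5% vs 15%, a Fisher test would miss it more often than not. Another is that the table needs only data already collected, which sections 5.1.3 and 10 leave unsettled. The last is that dislodgement shifts the T3 date. T3 is tied to removal of all drains, so this is conceivable, but the documents say only that the event may cause pain and require re-insertion.

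**Conclusion.** The point holds in limited form. The protocol names specific potential harms of a garment not previously studied, collects adverse events, and then plans no by-arm summary of them. The gap lies in analysis and reporting, chiefly of dislodgement, re-insertion and drain-site infection; it is not a failure of safety monitoring. Local breast and skin symptoms are already partly covered by the QLQ-BR23.

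The remedy should be described modestly. On the assumed 74-75 per arm, an arm with no events would still be compatible with a true rate of up to about 4% (one-sided 95%) or just under 5% (two-sided). Power for even an 8-point excess (2% vs 10%) is about 40%. These figures rest on 1:1 allocation, full enrolment of 149 and illustrative event rates. The textual finding depends on none of them. The primary test is not affected.

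**What to change.** Replace the entry in 13.7.1 with a descriptive harms summary for all randomized participants, reported beside the efficacy result:

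- By arm, the number and percent with (a) any adverse event, (b) drain dislodgement or unplanned re-insertion, (c) drain-site infection. Give exact 95% confidence intervals for each arm and a confidence interval for the risk difference.
- Skin reaction and overheating listed descriptively from the adverse event forms, with a note that unblinded reporting may differ by arm and that usual-care participants are not given the jacket.
- A statement that the table is descriptive and not a powered safety comparison.

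Reconcile section 5.1.3 with the calendar in section 10, so that the T3 record review either includes complications or does not. If (b) and (c) are to be drawn from it, define them and abstract them in the same way and over the same period in both arms.

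The cost is a short wording change, one table and, if complications are not now abstracted, a few added fields in the record review. Sample size, alpha and power do not change. The small downside is wide intervals, which the text should acknowledge in advance so that an absence of events is not read as evidence of safety.

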13.7.2 Evaluation of the Primary Efficacy Endpoint

Efficacy will be established if a statistically significant difference of 1.0 or greater on the PINS is detected.

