2.5 Preliminary Data

A preliminary survey study was conducted to explore self-reported pain intensity levels (just before discharge to ambulatory care) in patients post mastectomy in the Boston area. The sample (n=88) had a nearly equal distribution of age above and below 50 years; most were college educated and married/partnered. Of the 88 participants, 39% reported moderate to severe pain intensity, 53% reported pain several times a week to constantly, and 34% reported pain intensity as fair to almost unbearable soon after surgery. Sixty percent of participants had received a bilateral mastectomy, and 43% of these had bilateral implant reconstruction. Mean scores on the 0-10 pain intensity scale were 5.26 (SD=2.28) for those who had bilateral mastectomy and 2.5 (SD=2.13) for those having single mastectomy; participants who had reconstruction at the time of surgery pain averaged 4.98 (SD=2.18).

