13.2 Sample Size, Accrual Rate and Study Duration

The primary objective of this study will be to compare pain intensity (measured on the 0-10 scale, PINS) at the follow-up clinic appointment when all drains are removed (T3) between those randomized to UC or Jacki groups. A reduction of 1.0 on the PINS is thought to be clinically significant. With a sample size of 130 there is 80% power to detect a 1-point difference in PINS between UC and Jacki groups using a Wilcoxon rank sum test at the 2-sided 0.1 significance level assuming a standard deviation of 2.2 from

the preliminary study. The following table depicts the impact on power if the standard deviation at the follow-up visits is smaller or larger than estimated.

Standard Deviation	Power
1.8	91%
2.0	86%
2.2	80%
2.4	74%
2.6	68%

With a projected 13% rate of attrition, a total of 149 participants enrolled will yield an analytic sample of 130 evaluable participants. This number of participants will be accrued and will complete data collection within 10 months, based on clinical volume .

Accrual Targets				
Ethnic Category	Sex/Gender			
	Females	Males	Total	
Hispanic or Latino	39	+ 0	=	39
Not Hispanic or Latino	91	+ 0	=	91
Ethnic Category: Total of all subjects	130	+ 0	=	130
Racial Category				
American Indian or Alaskan Native	0	+ 0	=	0
Asian	6	+ 0	=	6
Black or African American	13	+ 0	=	13
Native Hawaiian or other Pacific Islander	0	+ 0	=	0
White	111	+ 0	=	111
Racial Category: Total of all subjects	130	+ 0	=	130

No interim analyses are planned due to the short duration, minimal risk, and minimal burden of the study. There are no early stopping rules.

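### Read literally, the efficacy rule in 13.7.2 needs significance and a detected difference of at least 1.0 with no estimator named, while the 80% power in 13.2 covers significance alone

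*Combined protocol and SAP*

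**What the plan says.** Section 13.7.2 states the criterion for success: "Efficacy will be established if a statistically significant difference of 1.0 or greater on the PINS is detected". Section 13.2 gives the power: "With a sample size of 130 there is 80% power to detect a 1-point difference in PINS between UC and Jacki groups", for a Wilcoxon rank sum test at two-sided 0.10 with SD 2.2. It also says that "A reduction of 1.0 on the PINS is thought to be clinically significant".

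Section 13.5 names the primary test: "The T3 pain score will be compared between UC and Jacki groups using a Wilcoxon rank sum test". It then allows an alternative: "Depending on the structure of the data, a t-test may be considered with a possible transformation", with the safeguard that "Assumptions will be examined and a method selected prior to testing". A further analysis is optional: "Additionally an analysis of covariance (ANCOVA) approach may be considered". The same section notes that scores are whole numbers and will be tied.

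Neither 13.5 nor 13.7.2 says whether the 1.0 refers to a difference in means, a difference in medians or a Hodges-Lehmann shift. No section gives the power of the two conditions together.

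**The concern.** Two gaps meet in one sentence.

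- **Power.** Someone who reads 13.2 and then 13.7.2 would expect a jacket that truly lowers pain by 1.0 point to be declared effective 80% of the time. If the detected difference must itself reach 1.0, that expectation is wrong for a difference in means.
- **Estimator.** The Wilcoxon test gives a p-value but does not itself define a difference in points. The 1.0 therefore has to be applied to some separate estimate, and the plan does not say which. On a whole-number scale the choice can turn the 1.0 condition from the governing one into one that hardly matters.

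At stake is the trial's headline conclusion. A significant result with a mean difference between about 0.64 and 1.0 fails the literal rule but succeeds if 1.0 was only the design effect.

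**Working it through.** **Inputs.** From 13.2: 130 evaluable, SD 2.2 (tabulated range 1.8 to 2.6), difference 1.0, two-sided alpha 0.10, Wilcoxon test. From 13.7.2: the 1.0 threshold. Assumed, because no ratio is stated: 1:1 allocation, 65 per arm.

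**Step 1: reproduce the plan's power.** Use the normal formula for two means, with n per arm multiplied by the Wilcoxon efficiency 3/π: 65 × 3/π = 62.07. Then SE = 2.2 × √(2/62.07) = 0.395, and power = Φ(1/0.395 − 1.645) = 81.3%, against 80% stated. All five rows of the plan's table agree within 2 points (see the table in step 3). The 80% is sound for significance.

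**Step 2: which condition governs, on means.**
- SE of the mean difference = 2.2 × √(2/65) = 0.386.
- Smallest significant mean difference, by the t approximation: t(0.95, 128) × SE = 0.639. This is below 1.0, so the 1.0 condition is the stricter one.
- At a true difference of 1.0: P(estimate ≥ 1.0) = 50%.
- True difference for 80% on the joint rule: 1 + 0.8416 × 0.386 = 1.32.
- No true effect: P(Z ≥ 1/0.386 = 2.59) = 0.48%, against 5% in favour of Jacki for significance alone.

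**Step 3: the tabulated SDs.** The simulated columns use continuous scores, a true difference of 1.0, 20,000 runs per setting and significance in favour of Jacki.

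| SD | Power in plan | Formula | Significance needs | Simulated: significant | Simulated: joint rule, means | True difference for 80% joint |
|---|---|---|---|---|---|---|
| 1.8 | 91% | 92.7% | 0.523 | 92.3% | 49.7% | 1.27 |
| 2.0 | 86% | 87.3% | 0.581 | 86.4% | 49.5% | 1.30 |
| 2.2 | 80% | 81.3% | 0.639 | 80.5% | 49.8% | 1.32 |
| 2.4 | 74% | 75.1% | 0.698 | 74.5% | 50.2% | 1.35 |
| 2.6 | 68% | 69.1% | 0.756 | 68.7% | 50.2% | 1.38 |

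At SD 2.2, 80.5 − 49.8 = 30.7% of trials are significant but fall short of 1.0 on means.

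**Step 4: the estimator, on whole-number scores.** Model: normal scores with SD 2.2, rounded and clipped to 0-10, tie-corrected Wilcoxon test. The plan gives no T3 mean, so the usual-care (UC) latent mean is assumed and varied.

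True mean difference set to exactly 1.0:

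| UC latent mean | Significant | Joint, means | Joint, medians | Joint, Hodges-Lehmann | Means and Hodges-Lehmann verdicts differ |
|---|---|---|---|---|---|
| 5 | 81.5% | 50.0% | 77.8% | 81.5% | 31.6% |
| 4 | 84.1% | 50.9% | 80.3% | 84.1% | 33.2% |
| 3 | 88.8% | 50.9% | 85.3% | 88.7% | 37.8% |

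On whole-number scores the Hodges-Lehmann estimate mostly takes whole-number values, so in these settings a significant result nearly always carries an estimate of at least 1.0. This weakens near the floor of the scale. At a latent shift of 1.0:
- UC latent mean 5 / 4 / 3: significant 80.0 / 80.2 / 79.8%; joint on Hodges-Lehmann also 80.0 / 80.2 / 79.8%.
- UC latent mean 2: significant 77.8%; joint on Hodges-Lehmann 66.8%.
- UC latent mean 1.5: significant 77.5%; joint on Hodges-Lehmann 45.3%.

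With no true effect (UC latent mean 5 / 4 / 3), Jacki is declared effective in 0.4 / 0.5 / 0.3% of trials on means and 5.3 / 5.0 / 4.9% on Hodges-Lehmann.

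**The case against.** The strongest reply is that 13.7.2 merely echoes 13.2. Both speak of detecting a one-point difference on the PINS, so the sentence may mean no more than significance in a trial designed around 1.0. On that reading the 80% is the right figure and the fault is loose wording. This stands as a possible reading. The text does not confirm it, and the two readings give opposite verdicts for a significant mean difference between about 0.64 and 1.0.

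Second, about 50% arises whenever a threshold equals the true effect, and asking for both significance and a clinically relevant estimate is a legitimate, conservative rule. That also stands. The rule is not an error; what is missing is its power.

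Third, means are the natural estimator, since the plan's own PINS figures are means and SDs, for example "Mean scores on the 0-10 pain intensity scale were 5.26 (SD=2.28) for those who had bilateral mastectomy" in 2.5. That favours means but does not define the estimate for 13.7.2.

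Some stronger readings are tempting but unsupported:
- That the Hodges-Lehmann shift always empties the 1.0 condition. It does so at assumed UC latent means of 3 to 5 but not at 2 or below. Low T3 scores cannot be ruled out: 2.5 reports a mean of 2.5 before discharge after single mastectomy, and T3 comes later.
- That the two estimators disagree in up to 44% of trials. A figure that high (43.5%) arises at a latent shift of 1.0 and UC latent mean 3, where clipping cuts the true mean difference to 0.87.
- That the plan leaves the test open until the result is known, with ANCOVA as a rival basis for success. Section 13.5 requires the method to be chosen before testing, and it introduces ANCOVA as an addition.

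**Conclusion.** The point holds, conditionally, and should be fixed. Under the literal reading, and on means, the success rule is met about 50% of the time at a true difference of 1.0 for every tabulated SD. A true difference of about 1.32 is needed for 80% at SD 2.2. If 1.0 was only the design effect, no power mismatch remains, but 13.7.2 still needs rewording to say so.

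The missing estimator matters under the literal reading. Means and Hodges-Lehmann verdicts differ in about 32-38% of trials at a true mean difference of exactly 1.0. That range is model-based and rests on rounded, clipped normal scores with UC latent means of 3 to 5. The figures on means assume 65 per arm; the 50% needs only that the smallest significant difference lies below 1.0.

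A reader might infer that the sample size is wrong or that the trial has only 50% power. The documents do not support that: the 80% in 13.2 reproduces for the test it describes. The missing direction in 13.7.2 is minor, because 13.2 speaks of a reduction.

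**What to change.** State in 13.7.2 which rule is meant.

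- **If the 1.0 condition is kept:** name the estimator and direction, for example the UC-minus-Jacki difference in means on the untransformed 0-10 scale, with pain lower in Jacki. In 13.2, give the power of the joint rule beside the 80%: on means, about 50% at a true difference of 1.0 and 80% at about 1.32.
- **If 1.0 was only the design effect:** reword 13.7.2 to rest on significance at two-sided 0.10 in favour of Jacki, and report a named estimate with its 90% confidence interval against 1.0. Note that the false-positive rate in favour of Jacki is then about 5%, rather than about 0.5% under the literal rule on means.

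Either way the cost is a sentence in 13.7.2 and, if the condition is kept, one in 13.2. No extra patients, data or tests are needed. The price of the first option is a less favourable published power figure; the price of the second is the higher false-positive rate.
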